Urine pregnancy test (women) ⁿ		X		X	X	X	X	X	X					
TB test (QuantiFERON-TB Gold In-Tube) ^d	X													
Serology (hepatitis B and C, HIV-1/2 combination)	X													

Table 2. Schedule of Assessments - Phase 2 Proof of Concept (POC) Study

	Screen ^a	Enroll	Treatment Period Follow-up									Safety Follow-Up		
Days	-28 to -1	0	15 (± 3)	30 (± 3)	60 (± 3)	90 (± 3)	120 (± 3)	150 (± 3)	180 (± 3)	187 (± 3)	195 (± 3)	210 (± 3)	240 (± 3)	270 (± 3)
Visit Number	1	2	3	4	5	6	7	8	9	--	--	10	11	12
Stool sample ^o	X													
Spot urine for protein/creatinine ratio	X	X		X	X	X	X	X	X			X	X	X
Urinalysis	X	X		X	X	X	X	X	X			X	X	X
PK Labs^p														
Predose ^q		X		X	X	X	X	X	X					
Postdose			X							X	X	X	X	X

Abbreviations: ACR = American College of Rheumatology; ADA= anti-drug antibody; AE = adverse event; **CCI**; BILAG = British Isles Lupus Assessment Group; BP = blood pressure; C = complement; CD4+ = cluster of differentiation 4; CLASI = Cutaneous Lupus Area and Severity Index; CRP = C-reactive protein; C-SSRS = Columbia Suicide Severity Rating Scale; ECG = electrocardiogram; **CCI**; **CCI**; FSH = follicle stimulating hormone; HR = heart rate; HIV = human immunodeficiency virus; IgG = immunoglobulin G; IgM = immunoglobulin M; IL-21 = interleukin 21; IV = intravenous; nAb = neutralizing antibody; PGA = Physician’s Global Assessment; PK = pharmacokinetic; pSTAT3 = phosphorylated signal transducer and activator of transcription 3; RNA = ribonucleic acid; RNP = ribonucleoprotein; SAE = serious adverse event; SC = subcutaneous; **CCI**; SLEDAI-2K = SLE Disease Activity Index 2000; SLICC = Systemic Lupus International Collaborating Clinics; **CCI**; TB = tuberculosis; TDAR = T-cell dependent antigen response.

- ^a Screening assessments will be performed over more than 1 visit.
- ^b Concomitant use of oral corticosteroids: A maximum daily dose of 30 mg/day of oral CS will be acceptable for eligibility for the study, however, the daily dose must be tapered down to a maximum of 10 mg/day for at least 5 days prior to Day 0 (randomization day). See Section 5.6.1 for further details.
- ^c Randomization should occur after patient eligibility has been confirmed. The actual randomization procedure can be completed on Day -1 after eligibility confirmation or the morning of Day 0 prior to dosing for logistical purposes.

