5.4 Inclusion Criteria

Patients who meet the following criteria will be considered eligible to participate in this clinical study:

1. Men and women, ages 18 to 70 years, inclusive
2. Patients must be mentally capable of giving consent and there must be evidence of a personally signed and dated informed consent document indicating that the patient has been informed of all pertinent aspects of the study
3. Patients must have SLE as defined by meeting 4 of the Systemic Lupus International Collaborating Clinics (SLICC) classification criteria for SLE (with at least 1 clinical and 1 immunologic criterion or Lupus nephritis as the sole clinical criterion in the presence of ANA or anti-dsDNA antibodies), either sequentially or simultaneously
4. At screening, patients must have at least 1 of the following:
 - a. Elevated ANA \geq 1:80 via immunofluorescent assay at the central laboratory
 - b. Positive anti-dsDNA or anti-Smith (Sm) above the normal level as determined by the central laboratory
 - c. C3 or C4 below normal as determined by central lab

5. At screening, the SLE Disease Activity Index 2000 (SLEDAI-2K) must be ≥ 6 , including points from at least 1 of the following clinical components:
 - a. Arthritis, rash, myositis, mucosal ulcers, pleurisy, pericarditis, and vasculitis
 - i. Excluding parameters which require central laboratory results: (hematuria, pyuria, urinary casts, proteinuria, positive anti-dsDNA, decreased complement, thrombocytopenia, and leukopenia)
 - ii. Points from lupus headache and organic brain syndrome will also be excluded
6. On Day 0, the SLEDAI-2K must be ≥ 6 , including points from at least 1 of the following clinical components:
 - a. Arthritis, rash, myositis, mucosal ulcers, pleurisy, pericarditis, and vasculitis
 - i. Excluding parameters which require central laboratory results: (hematuria, pyuria, urinary casts, proteinuria, positive anti-dsDNA, decreased complement, thrombocytopenia, and leukopenia)
 - ii. Points from lupus headache and organic brain syndrome are also excluded
7. Patients must have at least 1 of the following manifestations of SLE, as defined by the BILAG criteria as modified for use in this study, which must be confirmed by the central data reviewer:
 - a. BILAG A or B score in the mucocutaneous body system
 - b. BILAG A or B score in the musculoskeletal body system due to active polyarthritis defined as follows:

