5.8 Deviation from Inclusion/Exclusion Criteria

Deviation from the inclusion or exclusion criteria will not be allowed. If deviation of inclusion/exclusion criteria is discovered after randomization, the investigator should contact the medical monitor for discussion. A decision will be made whether to allow a patient continue or withdrawal from the study medication.

See [Section 7.8](#) for additional details.

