6.2 Enrollment/Randomization and Day 0 Treatment

Randomization should occur after patient eligibility for enrollment has been confirmed by the central eligibility review.

The study site will obtain a randomization number when registering the patient in IWRS. All patients will receive BOS161721 or placebo according to the kit number assigned by the IWRS randomization scheme.

After randomization, procedures include:

- PROs: CCI [REDACTED]
- C-SSRS
- Laboratory evaluations (fasting):
 - Hematology and clinical chemistry
 - Direct Coomb's test (if indicated)
 - CD4+ count, total IgG and IgM levels, plasma CCI [REDACTED], plasma CCI [REDACTED] and CCI [REDACTED], whole blood for leukocyte immunophenotype
 - ADA
 - pSTAT3 (predose [trough] samples only in Phase 2)
 - CCI [REDACTED]
 - Whole blood RNA collection
 - CCI [REDACTED]
 - See [Table 1](#) and [Table 2](#) for details of PK sampling in the MAD and POC studies
 - Urine pregnancy test will be collected on WOCBP prior to study drug administration
 - Spot urine for protein/creatinine ratio
 - Urinalysis
- Concomitant medication documentation
- Documentation of AEs and SAEs (see [Section 7.2.2.5](#) on SAE reporting requirements)

- Full physical examination
- Vital signs (prior to PK blood draw, predose, and at 1 and 2 hours postdose on Day 0)
- 12-lead ECG (prior to PK blood draw)
- SLE-related indices (BILAG-2004 Index, SLEDAI-2K, ACR-28 joint count, CLASI, PGA)
- SLICC/ACR damage index
- Study drug administration:
 - Administration of BOS161721 or placebo will take place on-site, and is discussed in [Section 8.3](#)
- Injection site reaction assessment, predose, and 2 hours postdose

Procedures on Day 0 are listed in the Schedule of Assessments ([Section 4.3](#)), and details are provided in [Section 7](#).

All patients who are enrolled, randomized, and receive study drug, or undergo study-specific procedures should re consent with any updated versions of IRB/IEC approved informed consents during study participation as applicable and per institutional guidelines.

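### Inclusion criterion 6 needs a Day 0 SLEDAI-2K of at least 6, but Phase 2 sites may randomise on Day -1 and the Day 0 procedure list scores the index after randomisation

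*Protocol*

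**What the plan says.** Section numbers for the schedule, criteria and procedures are those of the appended V2.0 (Amendment 1). The matching V3.0 sections are not in the part of the protocol at hand. Sample size and analysis sets are cited from V3.0.

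- **Entry condition.** Section 5.4, criterion 6: "On Day 0, the SLEDAI-2K must be" at least 6. This is separate from criterion 5, which sets the same threshold at screening. Items that need central laboratory results do not count.
- **Order required.** Table 2 footnote c (Section 4.3) opens: "Randomization should occur after patient eligibility has been confirmed". Section 6.2 says: "Randomization should occur after patient eligibility for enrollment has been confirmed by the central eligibility review". Section 6.1 admits only patients whom central review has confirmed against the criteria. The V3.0 change log (Appendix 7) adds a Section 3.2 under which the patients randomised are those who meet all the criteria.
- **Timing allowed in Phase 2.** The same footnote c continues: "The actual randomization procedure can be completed on Day -1 after eligibility confirmation or the morning of Day 0 prior to dosing".
- **Day 0 sequence.** Section 6.2 introduces its list with "After randomization, procedures include", and the list contains "SLE-related indices (BILAG-2004 Index, SLEDAI-2K, ACR-28 joint count, CLASI, PGA".
- **Eligibility check.** Tables 1 and 2 mark the inclusion/exclusion row in the screening column only.
- **If a failure is found later.** Section 5.8 states: "Deviation from the inclusion or exclusion criteria will not be allowed". For a deviation found after randomisation, it then sends the investigator to the medical monitor for a decision on whether the patient continues study medication.

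**The concern.** An entry criterion does its work only if it can be tested before the patient is randomised. A site that uses the Day -1 option cannot test criterion 6 in time. A site that randomises on Day 0 and follows the listed order scores the index too late.

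A patient who then falls below 6 has already been randomised, and two outcomes are open:

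- **Not dosed.** The patient is outside the FAS, which V3.0 Section 8.2.1 limits to patients with at least one dose and a post-baseline efficacy evaluation. This is an avoidable post-randomisation exclusion.
- **Dosed.** The patient is an ineligible member of the primary analysis, by an individual decision under Section 5.8 and not by rule.

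**Working it through.** **The passages side by side, for each permitted randomisation time**

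| Randomisation | Day 0 SLEDAI-2K available? | Consistent with confirmed eligibility? |
|---|---|---|
| Day -1 (Phase 2 only) | No, it cannot exist yet | No |
| Morning of Day 0, Section 6.2 order followed | Scored after randomisation | No |
| Morning of Day 0, index scored first | Yes | Yes, but against the Section 6.2 list |

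The first row cannot be reconciled by any reading that keeps criterion 6 as an entry condition. The second follows from the heading of the Day 0 list. The third shows that compliance is possible, but only if the site departs from that list. Nothing in Tables 1 or 2 prompts it to, because no eligibility check is marked on Day 0.

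**Scope.** The Day -1 option is in Table 2 only. The Table 1 footnote for Phase 1b does not contain it. The Section 6.2 list and the screening-only check apply to both phases.

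**Version.** The V3.0 change log lists edits to Table 2 footnotes f, i, l and q, to some items of the Day 0 section, and to sub-bullet ii of criterion 6. It lists no change to footnote c or to the position of the SLEDAI-2K. The log covers significant changes only, so persistence is likely but not proven.

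**Does the sample size suffer?** The plan's own figure comes first. Inputs from V3.0 Section 8.1: 132 patients, 2:1 (88 and 44), 65% vs 40%, 2-sided alpha 0.10.

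- Pooled rate = (88 × 0.65 + 44 × 0.40)/132 = 0.567
- Null SE = √[0.567 × 0.433 × (1/88 + 1/44)] = 0.0915
- Alternative SE = √[0.65 × 0.35/88 + 0.40 × 0.60/44] = 0.0897
- Power = Φ[(0.25 − 1.645 × 0.0915)/0.0897] = Φ(1.11) = 0.866

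This agrees with the stated figure of more than 80%.

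The protocol gives no rate of Day 0 failure. As an assumption, let a share of the 156 randomised fail and not be dosed, on top of the 24 losses already planned (156 − 24 = 132) and with no replacement:

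| Assumed share | Patients | FAS | Power |
|---|---|---|---|
| 0% | 0 | 132 | 86.6% |
| 2% | 3 | 129 | 85.9% |
| 5% | 8 | 124 | 84.7% |
| 10% | 16 | 116 | 82.5% |

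Power stays above 80% throughout.

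**The case against.** The best defence is that the protocol puts eligibility first. Footnote c says so before it grants the Day -1 option, and the option itself is conditioned on eligibility confirmation. Sections 6.1 and 6.2 and the new V3.0 Section 3.2 say the same. A careful site would score the SLEDAI-2K on the morning of Day 0 and then randomise. This stands as far as it goes: the protocol does not intend to test eligibility late, and the point is a conflict between passages. It does not rescue the Day -1 option, because a condition that includes a Day 0 score cannot be met the day before.

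The version caveat also stands. The quoted text is from V2.0, so the finding needs a check against V3.0 Sections 3.4, 4.4 and 5.2.

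A reader might infer that the trial loses its stated power because criterion 6 failures cannot respond. If 10% of the FAS were dosed with no possibility of a 4-point fall, the rates would become 58.5% and 36.0%. The documents do not support that reading, for four reasons:

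- No failure rate is given.
- Criterion 6 excludes central-laboratory items, whereas SRI-4 uses the global SLEDAI-2K. A patient can fail the criterion and still have 4 or more points to lose.
- The fall below 80% at 10% depends on the formula: 0.793 with pooled variance, 0.808 with unpooled.
- For patients not dosed, V3.0 Section 8.1 already allows enrolment to be increased to reach 132 in the FAS.

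**Conclusion.** The contradiction is real and should be corrected. For Phase 2, the Day -1 option cannot coexist with criterion 6 and the requirement that eligibility be confirmed before randomisation. For both phases, the Day 0 list and the screening-only check point the wrong way.

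The consequence is avoidable: either post-randomisation exclusions or ineligible patients in the FAS, handled individually. How many cannot be said, because the protocol gives no Day 0 failure rate. No loss of stated power is claimed. The conclusion assumes that the V3.0 counterparts of these passages are unchanged, as the silence of the change log suggests.

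**What to change.** After checking V3.0 Sections 3.4, 4.4 and 5.2:

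1. Remove the Day -1 option from Table 2 footnote c, and state that IWRS randomisation takes place on Day 0 once criterion 6 has been confirmed.
2. In the Day 0 procedures, place the clinical SLEDAI-2K needed for criterion 6 before the randomisation step.
3. Add an inclusion/exclusion check to the Day 0 column of Tables 1 and 2.

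A patient who fails on Day 0 is then a screen failure under Section 6.1, not a randomised deviation. BILAG, PGA and the urine pregnancy test need not move, since no stated contradiction turns on their position.

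The cost is small. The SLEDAI-2K is already scored on Day 0, and criterion 6 needs no central laboratory result. Kits could no longer be assigned the day before, so the Day 0 visit may be slightly longer.

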5 POPULATION

5.1 Participant Recruitment

Advertisements approved by the IRB, and investigator databases, may be used as recruitment procedures for adult men and women with moderately to severely active SLE.

5.2 Number of Patients

Approximately 186 male and female patients are planned for enrollment, but may be adjusted upward according to the dropout (noncompliance) rate, which will be monitored in a blinded fashion in an ongoing basis. Approximately 30 patients will be randomized for the MAD Phase 1b study, and approximately 156 patients will be randomized in the POC Phase 2 study. Note that approximately 30 dropouts are assumed.

5.3 Patient Screening

This study can fulfill its objectives only if appropriate patients are enrolled. The following eligibility criteria are designed to select patients for whom protocol treatment is considered appropriate. All relevant medical and non-medical conditions should be taken into consideration when deciding whether this protocol is suitable for a particular individual. Patient eligibility will be reviewed and confirmed by the medical monitor or designee prior to randomization. Screening assessments (see the Schedule of Assessments [[Section 4.3](#)]) for this study must be performed between Day -28 and Day -1.

5.4 Inclusion Criteria

Patients who meet the following criteria will be considered eligible to participate in this clinical study:

1. Men and women, ages 18 to 70 years, inclusive
2. Patients must be mentally capable of giving consent and there must be evidence of a personally signed and dated informed consent document indicating that the patient has been informed of all pertinent aspects of the study
3. Patients must have SLE as defined by meeting 4 of the Systemic Lupus International Collaborating Clinics (SLICC) classification criteria for SLE (with at least 1 clinical and 1 immunologic criterion or Lupus nephritis as the sole clinical criterion in the presence of ANA or anti-dsDNA antibodies), either sequentially or simultaneously
4. At screening, patients must have at least 1 of the following:
 - a. Elevated ANA \geq 1:80 via immunofluorescent assay at the central laboratory
 - b. Positive anti-dsDNA or anti-Smith (Sm) above the normal level as determined by the central laboratory
 - c. C3 or C4 below normal as determined by central lab

5. At screening, the SLE Disease Activity Index 2000 (SLEDAI-2K) must be ≥ 6 , including points from at least 1 of the following clinical components:
 - a. Arthritis, rash, myositis, mucosal ulcers, pleurisy, pericarditis, and vasculitis
 - i. Excluding parameters which require central laboratory results: (hematuria, pyuria, urinary casts, proteinuria, positive anti-dsDNA, decreased complement, thrombocytopenia, and leukopenia)
 - ii. Points from lupus headache and organic brain syndrome will also be excluded
6. On Day 0, the SLEDAI-2K must be ≥ 6 , including points from at least 1 of the following clinical components:
 - a. Arthritis, rash, myositis, mucosal ulcers, pleurisy, pericarditis, and vasculitis
 - i. Excluding parameters which require central laboratory results: (hematuria, pyuria, urinary casts, proteinuria, positive anti-dsDNA, decreased complement, thrombocytopenia, and leukopenia)
 - ii. Points from lupus headache and organic brain syndrome are also excluded
7. Patients must have at least 1 of the following manifestations of SLE, as defined by the BILAG criteria as modified for use in this study, which must be confirmed by the central data reviewer:
 - a. BILAG A or B score in the mucocutaneous body system
 - b. BILAG A or B score in the musculoskeletal body system due to active polyarthritis defined as follows:
 - i. “BILAG A:” Severe Arthritis, (BILAG item number 41), manifested by observed active synovitis in ≥ 2 joints with marked loss of functional range of movements and significant impairment of basic activities of daily living that has been present on several days cumulatively over the past 4 weeks, including at the time of the screening visit. See [APPENDIX 5](#) for additional detailed specifications.
 - Basic ADLs are defined as the following activities which require assistance or assistive devices, (at least 1 must be present and documented in source):
 - Ambulation, toileting, grooming- including bathing and dressing; feeding oneself, (and not responsive to steroids up to 10 mg/day, antimalarials, NSAIDs)
 - ii. “BILAG B:” Moderate Arthritis, Tendonitis or Tenosynovitis, (BILAG item number 42), defined as tendonitis/tenosynovitis, or active synovitis in ≥ 1 joint, (observed or throughout history), with some loss of functional range of movements which lead to some loss of functional range of motion as manifested by effects on instrumental ADLs such as:

- Cooking, driving, using the telephone or computer, shopping, cleaning, etc, and has been present on several days over the last 4 weeks, and is present at the time of the screening visit
- c. If only one “B” and no “A” score is present in the mucocutaneous body system or in the musculoskeletal body system due to arthritis, then at least 1 “B” must be present in the other body systems for a total of 2 “B” BILAG body system scores
8. Patients must be currently receiving at least 1 of the following:
 - a. Administration for a minimum of 12 weeks, and a stable dose for at least 56 days (8 weeks prior to signing consent) of the following permitted steroid-sparing agents:
 - i. Azathioprine (AZA), mycophenolate mofetil or mycophenolic acid, chloroquine, hydroxychloroquine, or methotrexate (MTX)
 - b. Prednisone (or prednisone-equivalent) cannot exceed 30 mg/day at screening for a patient to be eligible and must be stable at a maximum of 10 mg/day for at least 5 days prior to Day 0 (randomization) (see [APPENDIX 3](#))
 9. Women of childbearing potential (WOCBP; see [Section 5.7](#) for full information regarding WOCBP, definition of menopause, and contraception):
 - a. Must have a negative serum pregnancy test at screening. Urine pregnancy test must be negative prior to first dose
 - b. Must not be breastfeeding
 - c. Must agree to follow instructions for method(s) of contraception for the duration of treatment with study drug plus 5 half-lives of study drug BOS161721 plus 30 days (duration of ovulatory cycle) for a total of 36 weeks after treatment completion
 10. Men who are sexually active with WOCBP must agree to follow instructions for method(s) of contraception for the duration of treatment with study drug plus 5 half-lives of BOS161721 plus 90 days (duration of sperm turnover) for a total of 44 weeks after treatment completion
 11. Patients must demonstrate willingness and ability to comply with the scheduled study visits, treatment plans, laboratory tests, and other procedures

5.5 Exclusion Criteria

Patients presenting with any of the following will not be included in this study:

1. Drug-induced SLE, rather than “idiopathic” SLE
2. Other systemic autoimmune disease (eg, erosive arthritis, rheumatoid arthritis [RA], multiple sclerosis [MS], systemic scleroderma, or vasculitis not related to SLE)
 - a. RA-Lupus overlap (Rupus), and secondary Sjögren syndrome are allowed
3. Any major surgery within 6 weeks of study drug administration, (Day 0), or any elective surgery planned during the course of the study

4. Any history or risk for tuberculosis (TB), specifically those with:
 - a. Current clinical, radiographic, or laboratory evidence of active TB
 - b. History of active TB
 - c. Latent TB defined as positive QuantiFERON-TB Gold In-Tube (QFT-G) or other diagnostic test in the absence of clinical manifestations. Latent TB is not excluded if the patient has documented completion of adequate course of prophylactic treatment with regimen recommended by local health authority guideline, or the patient has started treatment with isoniazid, or other regimen recommended by local health authority guidelines for at least 1 month before Day 0 and continues to receive the prophylactic treatment during study until the treatment course is completed.
5. Active or unstable lupus neuropsychiatric manifestations, including but not limited to any condition defined by BILAG A criteria, with the exception of mononeuritis multiplex and polyneuropathy, which are allowed
6. Severe proliferative lupus nephritis, (WHO Class III, IV), which requires or may require induction treatment with cytotoxic agents or high dose CS
7. Concomitant illness that, in the opinion of the investigator, is likely to require additional systemic glucocorticosteroid therapy during the study, (eg, asthma), is exclusionary
 - a. However, treatment for asthma with inhalational CS therapy is allowed
8. Use or planned use of concomitant medication outside of standard of baseline treatment for SLE from Day -1 or for any time during the study. (See [Section 5.6](#) for prohibited concomitant medication)
9. Active and clinically significant infection (bacterial, fungal, viral, or other) within 60 days prior to first dose of study drug. Clinically significant is defined as requiring systemic antibiotics or hospitalization
10. A history of opportunistic infection, or a history of recurrent or severe disseminated herpes zoster or disseminated herpes simplex within the last 3 years
11. Chronic viral hepatitis including hepatitis B (HBV) and hepatitis C (HCV), known human immunodeficiency virus (HIV), or acquired immunodeficiency syndrome (AIDS)-related illness
12. Cryptosporidium in the stool sample at screening
13. White blood cells (WBC) $< 1,200/\text{mm}^3$ ($1.2 \times 10^9/\text{L}$) at screening
14. Absolute neutrophil count (ANC) $< 500/\text{mm}^3$ at screening
15. CD4+ count $< 500/\mu\text{L}$ at screening
16. Platelets $< 50,000/\text{mm}^3$ ($50 \times 10^9/\text{L}$) or $< 35,000/\text{mm}^3$ ($35 \times 10^9/\text{L}$) if related to SLE, at screening
17. Hemoglobin < 8 g/dL or < 7 g/dL at screening if due to anemia related to SLE
18. Proteinuria > 3.0 g/day (3000 mg/day) at screening or equivalent level of proteinuria as assessed by protein/creatinine ratio (3 mg/mg or 339 mg/mmol)

19. Serum creatinine > 2.0 mg/dL at screening or creatinine clearance (CrCL) < 40 ml/minute based on Cockcroft-Gault calculation³⁹:

$$\text{GFR} = ([1 \text{ for male}] \text{ or } [0.85 \text{ for female}]) \times (140 - \text{Age}) \times \text{BW} / (72 \times \text{Creatinine})$$

20. Serum ALT and/or serum AST > 2 × ULN at screening, unless explicitly related to lupus based on the investigator's judgment
21. Creatinine kinase (CK) > 3.0 × ULN at screening, unless it is related to lupus myositis
22. Direct bilirubin > 1.5 × ULN at screening (unless related to Gilbert's syndrome)
23. Any other laboratory test results that, in the opinion of the Investigator, might place a patient at unacceptable risk for participating in this study
24. History of allergic or anaphylactic reaction to any therapeutic or diagnostic monoclonal antibody (eg, IgG protein) or molecules made of components of monoclonal antibodies
25. History substance and/or alcohol abuse or dependence within the past 1 year, at the investigator's judgment
26. History of cancer within the last 5 years (except for cutaneous basal cell or squamous cell cancer, or cervical cancer in situ resolved by excision)
27. Any other severe acute or chronic medical or psychiatric condition, including recent (within the past year) medical conditions (eg, cardiovascular conditions, respiratory illnesses) that may increase the risk associated with study participation or investigational product administration or may interfere with the interpretation of study results and, in the judgment of the investigator, would make the patient inappropriate for entry into this study
28. Investigational site staff members directly involved in the conduct of the trial and their family members, site staff members otherwise supervised by the investigator, or patients who are employees of the sponsor or directly involved in the conduct of the trial
29. Currently participating in, or who have participated in other interventional (drug or device) clinical study within 30 days or 5 half-lives of baseline, whichever is longer
30. Recent (within the past 12 months) or active suicidal ideation or behavior based on patient responding "yes" to question 3, 4 or 5 on the Columbia Suicide severity Rating Scale (C-SSRS)
31. Current or pending incarceration
32. Current or pending compulsory detainment for treatment of either a psychiatric or physical (eg, infectious disease) illness

